5.5 Treatment Compliance

The Investigational Product will be administered to study patients by the study staff. Therefore, no patient compliance measures with regard to the Investigational Product are necessary.

All used and unused Investigational Product will be retained for verification by the Study Monitor.

5.6 Description of Treatments

5.6.1 SAN-300 for Subcutaneous Injection

The Investigational Product for SC injection (SAN-300-F02) is manufactured by IntegrityBio, Inc of Camarillo, CA, USA under Good Manufacturing Practice (GMP). The SAN-300-F02 drug product is formulated with 180 mg/mL anti-VLA-1 mAb, 30 mM histidine, 250 mM sorbitol, and 0.01% polysorbate

Santarus, Inc.
SAN-300 Clinical Trial Protocol: C2013-0302

Amendment 5: 28 Mar 2016

20 at pH 6. The drug product is filled to a total volume of 1 mL in a 2-mL USP type I glass vial with a 13-mm chlorobutyl stopper and a 13-mm aluminum seal. The storage temperature for the drug product is 2 °C to 8 °C, protected from light.

For SC administration, the appropriate volumetric dose of SAN-300 will be injected with a 27-gauge, ½ inch syringe needle on a weight-based calculation. More than one SC injection may be required (maximum volume of 1.2 mL per injection) depending on the total dose administered and the weight of the individual patient.

5.6.2 Placebo for Subcutaneous Injection

For SC administration, placebo is 30 mM histidine, 250 mM sorbitol, 0.01% polysorbate 20, and 3 μ g/mL riboflavin at pH 6, with a 1-mL fill in the same container closure system as the drug product. This was also manufactured by IntegrityBio, Inc of Camarillo, CA, USA under GMP. The appropriate volumetric dose of placebo will be injected with a 27-gauge, ½ inch syringe needle via SC injection. The volume of placebo administered SC will match the volume according to the weight-based calculations as if SAN-300 were to be administered. More than one SC injection may be required (maximum volume of 1.2 mL per injection) depending on the total dose administered and the weight of the individual patient. The intended storage temperature for the placebo product is 2 °C to 8 °C, protected from light.

5.7 Packaging and Labeling

Packaging, labeling, and shipping of study drug will be done by Catalent Pharma Solutions, LLC, located in Kansas City, MO, USA. Contracted regional drug distribution facilities will provide drug supplies to the investigational study centers.

5.8 Storage and Accountability

5.8.1 Receipt of Supplies

When supplies of study materials are received by the unblinded study personnel, he/she will acknowledge receipt by signing and dating documentation enclosed with the shipment, and returning it as instructed on the documentation. A copy will be retained for the Investigator File.

5.8.2 Storage of Supplies

Study materials will be stored by the study personnel according to the documentation provided with the study materials. The Sponsor reserves the right to inspect the Investigational Product storage area before and during the study. A written record will be made of the storage condition of the study materials and retained for the Investigator File.

5.8.3 Control of Supplies

Dispensing of the Investigational Product will be carefully recorded on appropriate Investigational Product accountability forms and will be verified periodically by an unblinded Study Monitor.

The accountability logs should include dates, quantities, batch numbers, expiration dates (if applicable), and any unique numbers assigned to the patient. The accountability logs will also include general

Amendment 5: 28 Mar 2016

details related to the study, including the Protocol/Amendment number, Sponsor, indication, and the Investigator.

5.9 Investigational Product Retention

The Investigator must maintain accurate records demonstrating dates and amount of Investigational Product received and dispensed and accounts of any Investigational Product accidentally or deliberately destroyed. Sufficient quantities of study drug will be kept by the Sponsor to reconfirm specifications if the need arises. These samples should be retained until the analyses of study data are complete or as required by the applicable regulatory requirement.

An unblinded Study Monitor will review the Investigational Product accountability logs and check all Investigational Product returns (both unused and used) before authorizing the destruction of used Investigational Product by the study site.

Amendment 5: 28 Mar 2016

6 CONCOMITANT THERAPY

The efficacy and safety of immunization during periods of SAN-300 therapy have not been adequately studied. It is recommended that a patient's vaccination record and possible vaccination requirements be reviewed and, if necessary, the patient be administered any required vaccination or booster at least 4 weeks before randomization. Review of the patient's immunization status and their need for the following vaccinations is recommended: tetanus; diphtheria; influenza; pneumoccocal polysaccharide; varicella; measles, mumps, and rubella; and hepatitis B vaccines. Immunization with a live vaccine is specifically prohibited within 4 weeks before randomization and throughout the study.

Folic acid \geq 5 mg/week (or an equivalent dose of folinic acid) is required for all patients.

Patients must remain on a stable dose of methotrexate (\geq 15 mg/week and \leq 25 mg/week) for \geq 6 weeks before randomization; a lower dosage of methotrexate (\geq 10 mg/week) is allowed if there is documented intolerance to dosages of \geq 15 mg/week. If taking hydroxychloroquine in combination with methotrexate, the patient must remain on a dose of \leq 400 mg/day hydroxychloroquine that has been stable for \geq 6 weeks before randomization. Note: If discontinued from hydroxychloroquine, the patient must remain on the revised treatment regimen for at least 4 weeks before randomization.

All other DMARDs are to be discontinued for at least the following periods of time:

- Oral DMARDs and etanercept at least 4 weeks before randomization
- Rituximab and any other B-cell/lymphocyte-depleting therapy at least 1 year before randomization
- All other biologic DMARDs, including infliximab, adalimumab, golimumab, certolizumab pegol, abatacept, and tocilizumab, at least 8 weeks before randomization
- Patients who have been on leflunomide must have leflunomide withdrawn for at least 4 weeks before randomization and must undergo treatment to facilitate drug elimination with 8 g cholestyramine three times daily for 3 days to be eligible for participation

Patients receiving treatment with prednisone (or equivalent dose of another corticosteroid) that is either over 10.0 mg/day or is not stable for at least 4 weeks before randomization are to be excluded. Intra-articular corticosteroid injection(s) are not permitted within 4 weeks of randomization and should not be given during the course of the study.

Patients receiving treatment with opioids or other narcotics are to be excluded. Note: Patients receiving NSAIDS or the following opioids (tramadol, codeine and oral acetaminophen/codeine combination) at stable doses for at least 2 weeks prior to randomization will be eligible for inclusion.

Patients are to remain on their stable RA treatment regimen (i.e., the RA treatment they are receiving at the time of randomization) throughout the course of the study, including the Follow-up Period. Concomitant use of other anti-arthritic treatments, including approved or experimental agents, therapies, or devices is not permitted.

All patients should be instructed not to start taking any new medications or therapies, including non-prescribed drugs, unless they have received permission from the Investigator. Any medication and any non-drug therapy or procedure used starting from signing of the Informed Consent Form (ICF) until

Santarus, Inc.
SAN-300
CONFIDENTIAL
SINCE CONFIDENTIAL
Clinical Trial Protocol: C2013-0302

Amendment 5: 28 Mar 2016

the completion of the study must be recorded in the patient's CRF according to the instructions for CRF completion.

7 PATIENT WITHDRAWAL AND STUDY TERMINATION

7.1 Reasons for Withdrawal

Participation in the study is strictly voluntary. A patient has the right to withdraw from the study at any time for any reason. If he/she chooses to withdraw, the patient must inform the Investigator immediately and will be asked to make an Early Withdrawal Visit. If feasible, it is also highly recommended that the patient schedule a Follow-up Visit for a safety evaluation 4 weeks after their last dose of study drug. The Investigator has the right to terminate participation of any patient at any time if it is deemed to be in the patient's best interest. The reason and circumstances for premature discontinuation will be documented in the patient's electronic case report form (eCRF). Possible examples for reasons of premature study withdrawal include:

- Withdrawal of consent
- Intolerable AE
- Intake of non-permitted concomitant medication
- Significant non-compliance with the protocol
- Positive pregnancy test in a female patient
- Clinical or administrative reason consistent with the requirements of the protocol at the Investigator's discretion
- Clinically significant worsening of RA that, in the opinion of the Investigator, requires immediate, specific medical treatment

7.2 Procedures for Early Withdrawal

When it is determined that a patient should withdraw from the study, the reason(s) must be recorded, final assessments must be scheduled, and provisions for the continued treatment of RA within the standards of care must be discussed with the patient. Safety and study endpoint evaluations for the Early Withdrawal Visit (see Sections 10.2.6 and 10.3.1) will be performed as soon as possible after the decision is made to withdraw the patient.

Additional interventions (concomitant medications or therapies) may be prescribed as needed by the patient. The patient's history and preferences should be considered and discussed when prescribing a new medication for RA.

Appropriate medical follow-up with the patient should be conducted as clinically indicated after the Early Withdrawal Visit. Telephone contacts between the patient and the study staff should be conducted as frequently as needed.

If the patient is found to have an AE or clinically significant laboratory abnormality, the patient will be followed until the event/abnormality is resolved, or until the Investigator determines that further follow-up is no longer medically indicated. The responsible IEC/IRB should be notified of any AEs and/or circumstances leading to early withdrawal.

Amendment 5: 28 Mar 2016

If a patient is withdrawn from study participation because of pregnancy, Product Safety and IEC/IRB should be informed by the site within 24 hours of awareness. All pregnancies occurring in female patients must be reported. The pregnancy will be reported according to the procedures provided in Section 9.8. Should the patient have a spontaneous abortion or complications during the pregnancy, then the event must be captured as an SAE. Sites are obligated to follow the patient until the outcome of the pregnancy is known. The patient and/or her treating physician should be encouraged to report any future medical problems the child develops of which they become aware that are considered related to the study drug.

Patients who are randomized and who subsequently withdraw from the study will not be replaced.

7.3 Sponsor's Termination of Study

Santarus reserves the right to discontinue the study at any time for clinical or administrative reasons.

If the study is prematurely terminated or suspended for any reason, the Investigator must inform all study patients currently receiving study drug and assure appropriate follow-up. Santarus should promptly inform the Investigators/institutions and the regulatory authorities of the termination or suspension and the reason(s) for the termination or suspension in accordance with applicable regulations. The IEC/IRB should also be informed promptly and provided with the reason(s) for the termination or suspension by Santarus or by the Investigator/institution, as specified by the applicable regulatory requirement(s).

8 STUDY ASSESSMENTS

8.1 Demographic Data/Medical History

Demographic data, current medications (including existing RA therapy), and medical history will be recorded at Screening. In addition, a separate detailed RA history including date of diagnosis and all prior treatments will be recorded.

8.2 Physical Examination

The physical examination will be conducted according to the Schedule of Assessments provided in Appendix 2 and will include the following: examination of general appearance, skin, head, neck (including thyroid), eyes, ears, nose, throat, heart, lungs, abdomen, lymph nodes, extremities, and nervous system. Height will be recorded at Screening only.

8.3 Vital Signs

Vital signs will include the following: body temperature (°C), pulse, respiratory rate, blood pressure, and weight. Vital signs will be assessed at all study site visits. On visits when study drug is to be administered vital signs will be assessed before dosing and blood pressure and pulse will be assessed at the end of the 1 hour observation period. Vital signs should be assessed prior to any blood draws.

8.4 12-Lead ECG

A 12-lead electrocardiogram (ECG) will be collected according to the Schedule of Assessments provided in Appendix 2. Patients should be in a resting, supine position for 10 minutes before ECG

SAN-300 Amendment 5: 28 Mar 2016

collection. The Investigator (or a designated, qualified observer at the investigational site) will interpret the ECG using one of the following categories: within normal limits, abnormal but not clinically significant, or abnormal and clinically significant.

8.5 Clinical Laboratory Tests

8.5.1 Laboratory Parameters

Blood samples for clinical laboratory assessments will be collected according to the Schedule of Assessments provided in Appendix 2. Patients will be in a seated or in a supine position during blood collection. Safety and Screening laboratory tests will include those listed in Table 3 and will be performed at a central laboratory.

Santarus, Inc.
SAN-300 Clinical Trial Protocol: C2013-0302

Amendment 5: 28 Mar 2016

Table 3. List of Laboratory Tests

Hematology:

- Hematocrit (Hct)
- Hemoglobin (Hgb)
- Mean corpuscular hemoglobin (MCH)
- Mean corpuscular hemoglobin concentration (MCHC)
- Mean corpuscular volume (MCV)
- Platelet count
- Red blood cell (RBC) count
- White blood cell (WBC) count with differential (neutrophils, lymphocytes, monocytes, eosinophils, and basophils)

Urinalysis:

- Appearance
- Bilirubin
- Color
- Glucose
- Ketones
- Microscopic examination of sediment
- Nitrite
- Occult blood
- pH
- Protein
- Specific gravity
- Urobilinogen
- Urine human chorionic gonadotropin (hCG) (only for females of childbearing potential)

Additional Assessments:

- Serum Immunoglobulin
- Serum tryptase
- Histamine
- C-reactive protein (CRP)
- Erythrocyte sedimentation rate (ESR) (conducted at site)

Serum Chemistry:

- Albumin (ALB)
- Alkaline phosphatase (ALK-P)
- Alanine aminotransferase (ALT; SGPT)
- Aspartate aminotransferase (AST; SGOT)
- Blood urea nitrogen (BUN)
- Calcium (Ca)
- Carbon dioxide (CO₂)
- Chloride (CI)
- Creatinine
- Creatine kinase
- Gamma-glutamyl transferase (GGT)
- Globulin
- Glucose
- Lactate dehydrogenase (LDH)
- Phosphorus
- Potassium (K)
- Sodium (Na)
- Total bilirubin
- Direct bilirubin
- Total cholesterol
- Total protein
- Triglycerides
- Uric acid
- Serum hCG (only for females of childbearing potential)

Coagulation:

- Prothrombin time (PT)
- Activated partial thromboplastin time (aPTT)
- International normalized ratio (INR)

Serology:

- Hepatitis B surface antigen (HBsAg)
- Hepatitis C virus (HCV) antibodies
- Human immunodeficiency virus (HIV) antibodies
- QuantiFERON[®]-TB Gold test (QFT)

Amendment 5: 28 Mar 2016

8.6 Pharmacokinetic Assessments

For patients in each cohort, serum SAN-300 concentrations will be determined from blood samples collected according to the Schedule of Assessments provided in Appendix 2 and the Specialty PK and PD Laboratory Testing Schedule provided in Appendix 3. Pharmacokinetic parameters for SAN-300 will be estimated using a population based approach with nonlinear mixed-effect modeling, in accordance with the FDA Draft Guidance on Population Pharmacokinetics (1999). Population PK methods will be used to estimate the relevant PK parameters for the population as well as for each patient who received SAN-300 and had sufficient blood samples in which SAN-300 was quantifiable. The details of the analysis will be documented in a Population Pharmacokinetic/Pharmacodynamic Analysis Plan.

8.7 Pharmacodynamic Assessments

The following PD parameters will be determined for all patients from blood samples collected at the same time as PK blood samples according to the Schedule of Assessments provided in Appendix 2 and the Specialty PK and PD Laboratory Testing Schedule provided in Appendix 3:

- VLA-1 receptor occupancy
- An immunophenotyping panel (CD3, CD4, CD8, CD14, CD19, CD45, CD45RO, and CD49α)
- Cytokines: IFNγ, TNFα, interleukin-6 (IL-6)
- CRP

Exploratory PK/PD modeling will be conducted as described in the Population Pharmacokinetic/Pharmacodynamic Analysis Plan.

8.8 Efficacy Assessments

Efficacy assessments will be conducted according to the Schedule of Assessments provided in Appendix 2 and will consist of Disease Activity Score for 28-joint count using C-reactive protein (DAS28-CRP), ACR Core Set Measurements, Health Assessment Questionnaire Disease Index (HAQ-DI), and MRI of the hand and wrist most clinically affected by RA.

8.8.1 DAS28-CRP Assessment

The DAS28 assessment is a standardized measure of improvement made using four components, two made by an assessor, one made by the patient, and one laboratory value (CRP), as shown below:

- Swollen and tender joint assessment (assessor refer to Appendix 6)
- Patient's global assessment of disease activity (patient)
- CRP (laboratory test)

The assessor will be an experienced rheumatology clinical assessor.

Amendment 5: 28 Mar 2016

8.8.2 ACR Core Data Set

The ACR Core Data Set is a standardized measure of arthritis activity consisting of seven measures, three made by an assessor, three made by the patient, and one laboratory value (CRP or ESR), as shown below:

- Swollen and tender joint assessment (assessor refer to Appendix 6)
- Physician's global assessment of disease activity (assessor)
- Patient assessment of pain (patient)
- Patient's global assessment of disease activity (patient)
- Patient's assessment of physical function as measured by Health Assessment Questionnaire (HAQ) (patient – Refer to Appendix 7)
- CRP or ESR (laboratory test)

The assessor will be an experienced rheumatology clinical assessor.

8.8.2.1 Physician's Global Assessment of Disease Activity

The physician's global disease assessment will be documented on a visual analogue scale (VAS) of 0 to 100 mm, ranging from 0 mm no disease activity to 100 mm (worst disease activity). The distance between the single vertical line marked by the physician will be measured in millimeters (mm) from the left end of the scale using a 100 mm ruler that will be provided. To standardize measurements, the same person should take the measurement wherever possible throughout the study.

8.8.2.2 Patient Assessment of Pain

Patients will be asked to rate their current pain intensity on a VAS. The VAS consists of a 100 mm-long scale ranging from 0 mm (no pain) to 100 mm (severe pain). The distance between the single vertical line marked by the patient will be measured in mm from the left end of the scale by the study staff, using the ruler provided.

8.8.2.3 Patient's Global Assessment of Disease Activity

Patient's global disease assessment will be documented on a VAS of 0 mm (no disease activity) to 100 mm (worst disease activity). The distance between the single vertical line marked by the patient will be measured in mm from the left end of the scale by the study staff, using the ruler provided.

A patient is considered to have an ACR20/50/70 response if there is an improvement of 20%/50%/70% in all of the following:

- Swollen joint count (66 joints)
- Tender joint count (68 joints) and
- At least three of the following five assessments:
 - Patient's assessment of pain
 - Patient's global assessment of disease activity
 - Physician's global assessment of disease activity
 - Patient's assessment of physical function, as measured by the HAQ-DI
 - CRP

Santarus, Inc.

SAN-300

Confidential
Clinical Trial Protocol: C2013-0302

Amendment 5: 28 Mar 2016

8.8.3 HAQ-DI Quality of Life Assessments

Quality of life will be assessed according to the Schedule of Assessments provided in Appendix 2 using the HAQ-DI (Appendix 7).

8.8.4 Magnetic Resonance Imaging of Hand and Wrist

The requirements for the Magnetic Resonance Imaging (MRI) scans are as follows:

- Magnet strength: 1.5 Tesla
- The same MRI scanner should be used for all scans of any individual patient throughout the study
- Region imaged: The hand with the most clinically affected metacarpophalangeal (MCP) joints and wrist at screening. Image will include the distal radioulnar joint. The same hand and wrist will be assessed for the follow up scan.
- Sequences will include T1-weighted 3D gradient echo (GRE) coronal scans pre- and post-gadolinium contrast, axial T1-weighted GRE scans post-contrast, and coronal STIR sequences.
- Exam time should last approximately 1 hour, including all patient setup and positioning

Using a central reader, all MRI scans will be assessed by two experienced rheumatology clinical assessors (see Appendix 8 for MRI scoring criteria) and their readings will be averaged to minimize any error due to the inherent variability of the MRI scoring process.

8.9 Other Laboratory Assessments

Additional laboratory parameters will be assessed according to the Schedule of Assessments provided in Appendix 2 and will include the following:

- Anti-SAN-300 antibody
- Rheumatoid factor (RF), antinuclear antibody (ANA), and anti-citrunillated peptide antibodies (ACPA)

8.10 Assessing Hypersensitivity

For suspected cases of anaphylaxis or hypersensitivity reactions, blood samples will be obtained for laboratory assessment of tryptase and histamine concentrations. In addition, Investigators should apply the criteria outlined in the National Institute of Allergy and Infectious Disease (NIAID) and the Food Allergy and Anaphylaxis Network (FAAN) second symposium on the definition of anaphylaxis report (Sampson, 2006), as outlined in Table 4, to assess patients for potential anaphylactic reactions.

Amendment 5: 28 Mar 2016

Table 4. Clinical Criteria for Diagnosing Anaphylaxis

Anaphylaxis is highly likely when any one of the following three criteria is fulfilled:

1. Acute onset of an illness (minutes to several hours) with involvement of the skin, mucosal tissue, or both (e.g., generalized hives, pruritus or flushing, swollen lips-tongue-uvula)

AND AT LEAST ONE OF THE FOLLOWING:

- a. Respiratory compromise (e.g., dyspnea, wheeze-bronchospasm, stridor, reduced PEF, hypoxemia)
- b. Reduced BP or associated symptoms of end-organ dysfunction (e.g., hypotonia [collapse], syncope, incontinence)
- 2. Two or more of the following that occur rapidly after exposure to a likely allergen for that patient (minutes to several hours):
 - a. Involvement of the skin-mucosal tissue (e.g., generalized hives, itch-flush, swollen lips-tongue-uvula)
 - b. Respiratory compromise (e.g., dyspnea, wheeze-bronchospasm, stridor, reduced PEF, hypoxemia)
 - c. Reduced BP or associated symptoms (e.g., hypotonia [collapse], syncope, incontinence)
 - d. Persistent gastrointestinal symptoms (e.g., crampy abdominal pain, vomiting)
- 3. Reduced BP after exposure to known allergen for that patient (minutes to several hours):
 - a. Infants and children: low systolic BP (age specific) or greater than 30% decrease in systolic BP*
 - b. Adults: systolic BP of less than 90 mm Hg or greater than 30% decrease from that person's baseline

PEF = peak expiratory flow; BP = blood pressure.

*Low systolic blood pressure for children is defined as less than 70 mmHg from 1 month to 1 year, less than $(70 \text{ mm Hg} + [2 \times \text{age}])$ from 1 to 10 years, and less than 90 mm Hg from 11 to 17 years.

Source: Sampson, 2006

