2.2 Secondary Objectives

The secondary objectives of this study are:

- To evaluate the PK and pharmacodynamics (PD) of repeat doses of SAN-300 in patients with active RA
- To evaluate the preliminary efficacy of repeat doses of SAN-300 in patients with active RA
- To evaluate the immunogenicity of repeat doses of SAN-300 in patients with active RA

Amendment 5: 28 Mar 2016

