10.2.3 Visits 3, 4, and 5 (Days 8, 15, and 22) Procedures

Patients should arrive at the study site having fasted for 4 to 6 hours. The following procedures will be performed at Visits 3 to 5:

- Record all medications (prescription and OTC) taken by the patient since previous visit
- Record all AEs since previous visit
- Record vital signs
- Perform a urine pregnancy test for all females of childbearing potential (Visit 5 only)
- Collect blood samples for:
 - CBC and chemistry
 - ESR (done at site with the kit provided)
 - CRP concentration
 - Anti-SAN-300 antibodies (Visit 3 only)
 - Serum SAN-300 concentration
 - Cytokine assessments (IFN_γ, TNFα, IL-6) (Visit 3 only)
 - Immunophenotyping panel (CD3/CD14/CD45RO/CD49a/CD45/CD4/CD19/CD8) (Visits 3 and 4 only)
 - VLA-1 receptor occupancy (Visits 3 and 4 only)
- Conduct the DAS28-CRP and ACR Core Set Measurements
- Administer the study drug appropriate to the randomization of the patient
- Complete the HAQ-DI
- Observe subject at minimum 1 hour post dose. Longer observation allowed if deemed necessary by investigator or designee
- Record blood pressure and pulse at the end of the 1 hour observation period
- Collect AEs since study drug administration

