10.2.5 Visits 6 and 7 (Days 29 and 36) Procedures

Patients should arrive at the study site having fasted for 4 to 6 hours. The following procedures will be performed at Visits 6 and 7:

Before Study Drug Administration during Visits 6 and 7:

- Record all medications (prescription and OTC) taken by the patient since previous visit
- Record all AEs since previous visit
- Record vital signs
- Perform a urine pregnancy test for all females of childbearing potential (Visit 7 only)
- Collect blood samples for:
 - CBC and chemistry
 - ESR (done at site with the kit provided)
 - CRP concentration
 - Serum SAN-300 concentration
 - Cytokine assessments (IFN_γ, TNFα, IL-6)
 - Immunophenotyping panel (CD3/CD14/CD45RO/CD49a/CD45/CD4/CD19/CD8)
 - VLA-1 receptor occupancy
- Conduct DAS28-CRP and ACR Core Set Measurements
- Complete HAQ-DI

Administer the study drug appropriate to the randomization of the patient.

After Study Drug Administration during Visits 6 and 7:

- Observe subject at minimum 1 hour post dose. Longer observation allowed if deemed necessary by investigator or designee
- Record blood pressure and pulse prior to the blood sample collection
- Collect blood samples at 1 hour post dose (Visit 7 only) for:
 - Serum SAN-300 concentration
 - Cytokine assessments (IFN_γ, TNFα, IL-6)
- Collect AEs since study drug administration

10.2.6 Visit 6A (between Days 30 to 32), Visit 7A (between Days 37 to 39), and Visit 7B (between Days 40 to 42)

Patients will come to the study site at a random, scheduled time within each of these intervals to have blood samples collected for serum SAN-300 concentration and VLA-1 receptor occupancy.

Record all AEs and medications taken since previous visit.

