10.3 Follow-up Period (Days 43 to 71)

10.3.1 Visit 8A (Day 50) and Visit 9A (Day 64)

Patients will come to the study site to have blood samples collected for:

- Serum SAN-300 concentration
- VLA-1 receptor occupancy
- Immunophenotyping panel
- Anti-SAN antibodies (Visit 9A only)
- Record all AEs and medications taken since previous visit

10.3.2 Visit 9 (Day 57) and Visit 10 (Day 71) or Early Withdrawal Visit (Follow-up Period)

Patients should arrive at the study site having fasted for 4 to 6 hours. The following procedures will be performed at Visits 9 and 10 or at the Early Termination Visit for patients who discontinue study participation during the Follow-up Period:

Record all medications (prescription and OTC) taken by the patient since previous visit

Santarus, Inc.
SAN-300
Confidential
Clinical Trial Protocol: C2013-0302

Amendment 5: 28 Mar 2016

- Record all AEs since previous visit
- Perform a physical examination (Visit 10 and Early Termination only)
- Record vital signs
- Collect urine for urinalysis (Visit 10 and Early Termination only)
- Collect blood samples for:
 - CBC and chemistry
 - ESR (done at site with the kit provided)
 - INR, PT, aPTT (Visit 10 and Early Termination only)
 - Complement (C3, C4, and CH50) (Visit 10 and Early Termination only)
 - CRP concentration
 - Serum immunoglobulins (Visit 10 and Early Termination only)
- Conduct DAS28-CRP and ACR Core Set Measurements
- Complete the HAQ-DI

Amendment 5: 28 Mar 2016

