2.2.1.2 Secondary Endpoints

The secondary endpoints for this study are:

- Pharmacodynamic (PD) analysis of SAN-300
- Maximum plasma concentration (C_{max}) of SAN-300 by dose group
- Area under the plasma concentration-time curve over the dosing interval (AUC_{0-τ}) of SAN-300 by dose group
- The immunogenicity of repeat doses of SAN-300
- American College of Rheumatology 20 (ACR20) responder rate at the End-of-Treatment Visit
- DAS28-CRP \leq 3.2 and \leq 2.6 responder rates at the End-of-Treatment Visit
- ACR50 and ACR70 responder rates at the End-of-Treatment Visit
- Change in Health Assessment Questionnaire Disease Index (HAQ-DI) at the End-of-Treatment Visit
- Magnetic Resonance Imaging (MRI) findings of the hand and wrist most clinically affected by RA at the End-of-Treatment Visit

The details of the statistical analyses on pharmacokinetic (PK) data for the definition of related to PK analyses endpoints will be documented in a Population

Pharmacokinetic/Pharmacodynamic Statistical Analysis Plan (PSAP).

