8.4 Other Laboratory Evaluations

Other laboratory parameters include anti-SAN-300 antibody levels, rheumatoid factor (RF), antinuclear antibody (ANA), and anti-citrunillated peptide antibodies (ACPA). All other laboratory parameters will be summarized using descriptive statistics and presented by time point and treatment group. All other laboratory parameters will be presented for individual patients in data listings.

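### Anti-SAN-300 antibody has no scheduled sample between Day 8 and Day 43, at a suspected reaction or at follow-up withdrawal, and no per-patient treatment-emergent incidence is planned.

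*Protocol*

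**What the plan says.** **Objective.** Protocol 2.2 lists as a secondary objective: "To evaluate the immunogenicity of repeat doses of SAN-300 in patients with active RA". SAP 2.2.1.2 names "The immunogenicity of repeat doses of SAN-300" among the secondary endpoints. Neither document defines antibody positivity, baseline status, treatment-emergent status or a per-patient incidence.

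**Scheduled samples.** Protocol 10.2.1 takes antibody before the first dose. Section 10.2.3 restricts it, among Days 8, 15 and 22, to "Anti-SAN-300 antibodies (Visit 3 only"), and Appendix 3 shows this draw as pre-dose. The blood list under "The following procedures will be performed at Visits 6 and 7" (10.2.5, Days 29 and 36) does not include it. Section 10.2.7 includes it at Day 43 and at withdrawal during the Treatment Period. In follow-up, 10.3.1 has "Anti-SAN antibodies (Visit 9A only"), which is Day 64.

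**Event-driven samples.** For suspected anaphylaxis or hypersensitivity, 8.10 states that "blood samples will be obtained for laboratory assessment of tryptase and histamine concentrations". It names neither antibody nor SAN-300 concentration. Section 10.3.2 (Days 57 and 71, or withdrawal during follow-up) also lists neither. Section 7.1 recommends that a withdrawing patient "schedule a Follow-up Visit for a safety evaluation 4 weeks after their last dose of study drug", and specifies no antibody sample there.

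**Reporting.** SAP 8.4 puts antibody levels in one group with RF, ANA and ACPA: "All other laboratory parameters will be summarized using descriptive statistics and presented by time point and treatment group". Its next sentence provides for individual patient listings.

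**The concern.** The protocol gives reasons to expect antibody. Monkeys formed it on repeat dosing (1.2.2), and Phase 1 found two subjects with treatment-emergent antibody after single doses (1.3). This is the first repeat-dose study in patients, so two questions matter: how many patients develop antibody, and whether antibody goes with reactions.

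The schedule is thin where those questions would be answered. Day 8 follows one injection only, so no scheduled sample taken while dosing continues reflects repeat dosing. A patient who has a reaction and stays in the study has no antibody result near the event. A patient who leaves during follow-up loses the only sample taken four weeks or more after the last active dose.

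The planned summary is a separate problem. Tables by visit do not add up patients who are positive at different visits, and they do not separate antibody present before treatment from new antibody. Phase 1 was described in treatment-emergent terms, so the planned tables would not compare directly with it.

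**Working it through.** The documents give no expected rate or precision for immunogenicity, so there is no plan figure to reproduce. The check is a count of days and doses, followed by two illustrations.

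**1. The gap.** Antibody days are 1, 8, 43 and 64 (10.2.1, 10.2.3, 10.2.7, 10.3.1; Appendix 3 agrees). The gap is 43 − 8 = 35 days.

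**2. Active doses in the gap** (dosing days from 3.1; the Day 8 sample precedes the Day 8 dose).
- Weekly cohorts (A, B, E, F): Days 8, 15, 22, 29 and 36, so 5 of 6.
- Every-other-week cohorts (C, D): Days 15 and 29, so 2 of 3.

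**3. Distance from the last active dose.**

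| Sample | Weekly (last dose Day 36) | Every other week (last active dose Day 29) |
|---|---|---|
| Day 43 | 7 days | 14 days |
| Day 64 | 28 days | 35 days |

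A patient who leaves between Days 44 and 63 has Day 43 as the last antibody sample.

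**4. Wait for a patient who reacts and continues.** From a reaction on Day 15, 22, 29 or 36 to the Day 43 sample is 28, 21, 14 or 7 days. From a reaction after the Day 8 dose it is 35 days.

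**5. Drug level.** SAN-300 concentration is drawn before every dose (10.2.1, 10.2.3, 10.2.5, Appendix 3). Only a level at the time of the event and one at follow-up withdrawal are missing.

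**6. Tabulation, illustrated.** In an arm of 6, suppose one patient is positive only on Day 8 and another only on Day 64. Each visit shows at most 1/6 = 17%; ever positive is 2/6 = 33%. Both patients are caught by the schedule, so this measures the summary and says nothing about the gap.

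**7. Missed transient responses, illustrated.** Let p be the true ever-positive rate and f the share of positives missed. The chance of seeing at least one positive among 6 is 1 − (1 − p(1 − f))^6. Both p and f are assumptions. The lowest p is 2/46 = 4.3% from Phase 1 (45 healthy subjects plus 1 patient dosed), assuming that both positives had received SAN-300.

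| p | f = 0 | f = 0.25 | f = 0.5 |
|---|---|---|---|
| 4.3% | 0.234 | 0.180 | 0.124 |
| 10% | 0.469 | 0.374 | 0.265 |
| 20% | 0.738 | 0.623 | 0.469 |
| 30% | 0.882 | 0.783 | 0.623 |

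If Days 43 and 64 catch every response (f = 0), the gap costs nothing.

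**8. Cross-references.**
- 3.1 sends early withdrawers to the Exit Visit assessments, which have no antibody.
- 7.2 cites 10.2.6 and 10.3.1 for the Early Withdrawal Visit. Section 10.2.6 has no antibody, and 10.3.1 has it at Visit 9A only. The withdrawal procedures are in 10.2.7 and 10.3.2.
- 8.9 sends antibody to Appendix 2, which has no antibody row. The row is in Appendix 3.

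**The case against.** Baseline, Day 8, end of treatment and about four weeks after the last weekly dose is a reasonable schedule for an unpowered Phase 2a study with 6 patients per active arm. Persistent responses should show on Day 43 or Day 64. Phase 1 reported no immunogenicity-related events in its two positive subjects. Protocol 9.5 also lets investigators run, and Product Safety request, further tests when following up an adverse event. All of that stands, although 9.5 does not name antibody and leaves the draw to case-by-case judgement.

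A reader might infer more than the documents support:
- *That nobody is sampled between Day 8 and Day 43.* Section 10.2.7 takes antibody and SAN-300 concentration at withdrawal during the Treatment Period, so a patient who reacts and then leaves can be sampled soon afterwards.
- *That a patient who reacts has no drug level until Day 43.* Pre-dose levels are drawn at every dosing visit.
- *That antibody is reported only per visit.* Patient listings are planned, and a pre-dose Day 1 sample exists. Baseline status, ever-positive status and a match with the adverse event listings can all be derived by hand. What is missing is a definition fixed in advance and a table for a named secondary endpoint.
- *That immunogenicity will be understated.* The documents give no rate of transient antibody and nothing on how far circulating drug affects the assay.

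**Conclusion.** The point holds as a limited one. Immunogenicity may be understated, mainly for transient responses and, in the by-visit tables, for patients positive at different visits. For patients who react and stay in the study, antibody cannot be timed against the reaction. Patients who leave during follow-up before Day 64 have no late sample.

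The size of any understatement from the gap is unknown. At an assumed true rate of 20%, missing half of the positives would cut the chance of seeing any in an arm of 6 from 74% to 47%; missing none would leave it unchanged. The effect of the tabulation is certain in kind but recoverable from the listings. The conflicting withdrawal references add a practical risk: a site that follows 3.1 or 7.2 literally could omit the antibody sample that 10.2.7 requires.

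**What to change.** 1. **SAP 8.4 (the main change).** Report by arm the number of patients with treatment-emergent antibody at any post-baseline visit: negative at baseline then positive, or a titre rise if positive at baseline. List these patients against hypersensitivity events and SAN-300 concentration. This needs no new blood.
2. **Sampling, where still open.** Add antibody and SAN-300 concentration to the 8.10 reaction draw and to the 10.3.2 early-withdrawal draw. Antibody on the existing Day 22 or Day 29 draw would narrow the gap but is optional.
3. **Cross-references.** Reconcile 3.1, 7.2 and 8.9 with 10.2.7, 10.3.2 and Appendix 3, so that one set of early-withdrawal and antibody instructions applies.

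The cost is SAP wording, a protocol clarification, and a few extra tubes and assays for patients who react or leave. SAP 3.5 records 41 subjects already randomized, so the sampling changes cannot recover draws already missed in them. The SAP change still can be made on the data collected.
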